## **8.1 Screening period**

The Screening period must take place within 30 days prior to Randomization and include the Visit 1 (Screening) and the pre-dose assessments of Visit 2 (Day 1).

The start of the Screening period is defined as the day of the first Screening assessment (i.e., signature of informed consent).

### **8.1.1 Visit 1 (Screening)**

Visit 1 will be performed up to 30 days prior to Randomization. Visit 1 date is defined as the date of the first assessment performed for the study (i.e., informed consent signature).

During this visit, subject informed consent will be obtained, and the assessments required for subject eligibility will be performed. These assessments may generally be performed on separate days within the Screening period.

Visit 1 includes:

- After discussing the study with the investigator and after agreeing to participate, the subject must sign the ICF. It is the responsibility of the investigator to obtain written

informed consent prior to any screening assessment. Subjects will be assigned a subject number by the IRT provider, for identification throughout the study. In case of re-screening, the subject number assigned during the first screening procedure will be retained.

- Recording of demographics, medical history, smoking status, and disease history (including documented history of ANA, anti-dsDNA antibodies)
- Review of SLE diagnosis and ACR criteria
- Recording of previous SLE therapies, concomitant medications and background SLE therapies
- Complete physical examination
- Body weight, and height
- SLEDAI-2K and PGA
- CXR (any CXR performed within 90 days prior to Screening can be used). In case of re-screening, CXR does not need to be repeated.
- SBP/DBP (including supine and standing position to assess orthostatic hypotension; see exclusion criterion 13)
- 12-lead ECG
- 24-hour ECG-Holter (starting before 12:00)
- Echocardiography (under the responsibility of the echocardiography specialist)
- Spirometry (under the responsibility of the pulmonary function laboratory technician or expert)
- Ophthalmological examination (under the responsibility of the ophthalmologist)
- OCT (under the responsibility of the ophthalmologist)
- Hematology (including coagulation tests), blood chemistry, and serum pregnancy test for WOCBP
- Viral serology
- TB test
- ANA, anti-dsDNA antibodies, complement C3 and C4
- Urine protein-to-creatinine ratio
- Urinalysis (dipstick)
- Recording of AEs/SAEs: all AEs/SAEs occurring after signing of the ICF are to be reported in the eCRF and on an SAE form, if applicable.

The principal investigator / treating physician must check inclusion/exclusion criteria. The next visit (Visit 2) will only be scheduled if the subject meets all the eligibility criteria. Date of screen failure will be collected in the IRT system and in the eCRF; additionally, the reasons for screen failure are documented in the eCRF (screening information is collected for all screen failure subjects).

## 8.2 Treatment period

The treatment period consists of Visits 2 to 6 (Randomization – Day 1, Weeks 2, 4, 8, and 12 (EOT)).

### 8.2.1 Visit 2 – Randomization Day 1

Visit 2 corresponds to the start of the treatment period (Day 1 of the study). The ECGs (pre- and post-dose), BP (pre- and post-dose), and first-dose administration must be performed on the same day and define the date of the visit. This date should preferably correspond to the date of randomization in the IRT system. The assessments during this visit will be *divided* into two parts: before (pre-dose) and after study drug administration (post-dose).

Important note: For WOCBP, the serum pregnancy test at Visit 1 (Screening) must be performed at least 3 weeks before the urine pregnancy test performed at Visit 2 prior to Randomization.

#### 8.2.1.1 Visit 2 – Day 1 – pre-dose assessment

The principal investigator / treating physician must check all inclusion/exclusion criteria. Pre-dose assessments include:

- SF-36v2™ questionnaire (to be completed prior to any other assessment)
- Recording of change in concomitant medications and background SLE therapies since Visit 1
- Recording of methods of contraception (for WOCBP)
- Abbreviated physical examination
- SLEDAI-2K and PGA
- Pre-dose SBP/DBP (under the responsibility of the CSA)
- Pre-dose 12-lead ECG (under the responsibility of the CSA)
- 24-hour ECG-Holter starting immediately before first dosing (under the responsibility of the CSA)
- Hematology (including coagulation tests), blood chemistry
- Urine pregnancy test (for WOCBP)
- Additional serum sample for viral serology
- ANA, anti-dsDNA antibodies, complement C3 and C4
- Exploratory biomarkers
- Lymphocyte subsets
- Urine protein-to-creatinine ratio
- Urinalysis (dipstick)
- Recording of AEs/SAEs: all AEs/SAEs occurring after signing of the ICF are to be reported in the eCRF and on an SAE form, if applicable.

### ***8.2.1.2 Visit 2 – Day 1 – Randomization and post-dose assessment***

After confirmation of eligibility (i.e., verification of all entry criteria) by the investigator, randomization should occur via IRT to obtain randomization and study treatment kit numbers. Study treatment should then be dispensed and the subject should take the first dose of study treatment.

Visit 2 post-dose assessments include:

- Hourly 12-lead ECG and SBP/DBP assessments for 6 hours or until the patient meets the discharge criteria (under the responsibility of the CSA [see [Appendix 4](#)]). If discharge criteria are not met after 12 hours, the subject should be permanently discontinued.
- Recording of AEs and SAEs.

The subject will be instructed to contact the site if she/he has any questions or problems. WOCBP will be reminded to use the methods of contraception defined for this study. The reminders must be documented in the hospital chart.

An appointment for next visit will be scheduled and the subject will be instructed to:

- bring back the remaining study medication for drug accountability
- come fasted to the site
- not take study treatment on the day of study visit prior to coming to the site
- contact the principal investigator / treating physician immediately in the event of the appearance of any symptoms (e.g., suggestive of an SLE flare) or any AEs or SAEs or if a study treatment dose is missed.

### **8.2.2 Visit 3 – Week 2**

The time window for this visit is  $\pm 3$  days. The date of the visit will be registered by the investigator or study staff in the eCRF only (no IRT visit registration as no study drug dispensing at Visit 3). All assessments may be performed up to 3 days prior to or after this visit date. The visit includes:

- Recording of change in concomitant medications and background SLE therapies since Visit 2
- Recording of methods of contraception (for WOCBP)
- Abbreviated physical examination
- SBP/DBP
- 12-lead ECG
- Spirometry (under the responsibility of the pulmonary function laboratory technician or expert)
- Ophthalmological examination (under the responsibility of the ophthalmologist)

- Hematology (including coagulation tests), blood chemistry
- Urine pregnancy test (for WOCBP)
- Urinalysis
- PK sampling
- Study drug accountability for compliance review
- Recording of AEs and SAEs
- Remind WOCBP to use the methods of contraception defined for this study
- Schedule an appointment for the next visit and instruct the subject to:
  - bring back any remaining study medication for drug accountability
  - come fasted to the site
  - not take study treatment on the day of study visit prior to coming to the site (study drug will be taken at the clinical site)
  - contact the principal investigator / treating physician immediately in the event of the appearance of any symptoms (e.g., suggestive of an SLE flare) or any AEs or SAEs or if a study treatment dose is missed.

### 8.2.3 Visit 4 – Week 4 and Visit 5 – Week 8

The visit window for these visits is  $\pm 5$  days. The date of study treatment dispensing, preferably corresponding to the date of registration of the visit in the IRT system defines the date of the visit. All other assessments may be performed up to 5 days prior to or after this visit date. The visit includes:

- Recording of changes in concomitant medications and background SLE therapies since previous visit
- Recording of methods of contraception (for WOCBP)
- Abbreviated physical examination
- SLEDAI-2K and PGA
- SBP/DBP
- 12-lead ECG
- Spirometry (under the responsibility of the pulmonary function laboratory technician or expert)
- Ophthalmological examination (under the responsibility of the ophthalmologist)
- Hematology (including coagulation tests) and blood chemistry
- Urine pregnancy test (for WOCBP)
- ANA, anti-dsDNA antibodies, complement C3 and C4
- Exploratory biomarkers
- Urinalysis
- PK sampling
- Study drug dispensing and accountability

- Recording of AEs/SAEs
- Remind WOCBP to use the methods of contraception defined for this study
- Schedule an appointment for the next visit and instruct the subject to:
  - bring back any remaining study medication for drug accountability
  - come fasted to the site
  - not take study treatment on the day of study visit prior to coming to the site (study drug will be taken at the clinical site)
  - contact the principal investigator / treating physician immediately in the event of the appearance of any symptoms (e.g., suggestive of an SLE flare) or any AEs or SAEs or if a study treatment dose is missed.

#### 8.2.4 Visit 6 – EOT

The EOT visit will take place at Week 12 ( $\pm$  5 days) or earlier in case of premature discontinuation of study treatment. In all cases, the EOT visit must preferably take place 1 day after the last dose of study treatment intake but no later than 7 days after the last dose of study treatment intake. The visit includes:

- SF-36v2™ questionnaire (to be completed prior to any other assessment)
- Recording of changes in concomitant medications and background SLE therapies since Visit 5
- Recording of methods of contraception (for WOCBP)
- Complete physical examination
- Body weight
- SLEDAI-2K and PGA
- SBP/DBP
- 12-lead ECG
- Echocardiography (under the responsibility of the echocardiography specialist)
- Spirometry (under the responsibility of the pulmonary function laboratory technician or expert)
- Ophthalmological examination (under the responsibility of the ophthalmologist)
- OCT (under the responsibility of the ophthalmologist)
- Hematology (including coagulation tests) and blood chemistry
- Urine pregnancy test (for WOCBP)
- ANA, anti-dsDNA antibodies, complement C3 and C4
- Exploratory biomarkers
- Lymphocyte subsets
- Urine protein-to-creatinine ratio
- Urinalysis
- PK sampling

- Study drug accountability
- Recording of AEs/SAEs
- Remind WOCBP to use the methods of contraception defined for this study
- Schedule an appointment for the next visit and instruct the subject to:
  - come fasted to the site
  - contact the principal investigator / treating physician immediately in the event of the appearance of any symptoms (e.g., suggestive of an SLE flare) or any AEs or SAEs or if a study treatment dose is missed.

### **8.3 Follow-up period**

#### **8.3.1 Visit 7 – EOS**

The EOS visit will take place 6 weeks ( $\pm$  5 days) after last study treatment dose. The visit includes:

- Recording of changes in concomitant medications and background SLE therapies since Visit 6
- Recording of methods of contraception (for WOCBP)
- Abbreviated physical examination
- SLEDAI-2K and PGA
- SBP/DBP
- 12-lead ECG
- Spirometry (under the responsibility of the pulmonary function laboratory technician or expert)
- Ophthalmological examination (under the responsibility of the ophthalmologist)
- Hematology (including coagulation tests) and blood chemistry
- Serum pregnancy test (for WOCBP)
- ANA, anti-dsDNA antibodies, complement C3 and C4
- Exploratory biomarkers
- Lymphocyte subsets
- Urinalysis
- PK sampling
- Recording of AEs/SAEs

A urine pregnancy test will be dispensed to WOCBP.

#### **8.3.2 Visit 8 and Visit 9– follow-up (telephone contact visits)**

Eleven weeks  $\pm$  5 days and 16 weeks  $\pm$  5 days, after the last dose of study drug has been taken, telephone calls will be made and include:

- Recording of SAEs
- Urine pregnancy test for WOCBP (performed at home prior to telephone contacts with test kits dispensed at Visit 7 – EOS)

Note that the data reported at these visits will not be entered in the eCRF. Results of the urine pregnancy tests must be reported in the source data. SAEs will be reported to Global Drug Safety and will be presented separately in the Clinical Study Report.

#### **8.4 Unscheduled visits (U1, U2...)**

Unscheduled visits may be performed at any time during the study. These visits include (but are not limited to) those performed due to safety (e.g., occurrence of an AE, laboratory abnormalities), and/or SLE disease exacerbations (e.g., renal flare).

The date of the visit and the reason for such visits as well as any data related to study assessments performed at unscheduled visits will be recorded in the eCRF.

During an unscheduled visit, the following assessments must be performed:

- Recording of changes in concomitant medications and background SLE therapies since last visit
- Recording of AEs/SAEs

Additional assessments may be performed at the discretion of the investigator including but not limited to:

- Abbreviated physical examination
- SLEDAI-2K and PGA
- SBP/DBP
- 12-lead ECG
- Hematology (including coagulation tests) and blood chemistry
- Urine pregnancy test (for WOCBP)
- ANA, anti-dsDNA antibodies, complement C3 and C4
- Urine protein-to-creatinine ratio
- Urinalysis

Depending on the reason for the unscheduled visit (e.g., AE), additional assessments will be performed based on the judgment of the investigator, and the results will be recorded in the eCRF. For the additional assessments performed during unscheduled visit which are not part of the standard study assessments, results are not to be reported in the eCRF. However, any clinically relevant abnormalities detected must be reported as an AE or SAE as appropriate in the corresponding Adverse Event form of the eCRF. After an

unscheduled visit, the regular scheduled study visits must continue according to the planned visit and assessment schedule.

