**Confidential**

Periods	Name	Pre-randomization	Treatment period					FU			Unscheduled	
	Duration	Up to 30 days	12 weeks					16 weeks			NA	
Visits	Number	1	2	3	4	5	6	7	8	9	U1, U2,...	I
	Name	Screening	Randomization (15)	W2	W4	W8	EOT	EOS	Phone call FU	Phone call FU	Unscheduled (17)	Re-initiation
	Time	Day -30 to -1	Day 1	Week 2	Week 4	Week 8	Week 12 or earlier in case of premature discontinuation (16)	Last study treatment intake + 6 weeks	Last study treatment intake + 11 weeks	Last study treatment intake + 16 weeks	Any day between Day 1 and EOS	For study treatment interruptions that started up to Day 14
	Visit window			± 3 days	± 5 days	± 5 days	± 5 days	± 5 days	± 5 days	± 5 days	NA	
Additional serum sample for viral serology***			X									
ANA, anti-dsDNA antibodies, complement C3 and C4**		X	X		X	X	X	X			X	
Exploratory biomarkers** (10)			X		X	X	X	X				
Lymphocyte subsets*** (11)			X				X	X				
Urine protein-to-creatinine ratio**		X	X				X				X	
Urinalysis (dipstick)*		X	X	X	X	X	X	X			X	
PK sampling (pre dose)***				X	X	X	X	X				
Study treatment dispensing & accountability* (13)			X	X	X	X	X					X
AEs* (14)		X	X	X	X	X	X	X			X	X
SAEs* (14)		X	X	X	X	X	X	X	X	X	X	X

\* Data collected in the eCRF

\*\* Electronically transferred to sponsor

\*\*\* Sample collection date recorded in the eCRF (for PK samples, time will also be recorded)

Assessments in part A and B are identical.

Day 1 (date of Randomization visit) is to be used as the reference date for the purpose of calculating the subsequent visit dates (and time windows).

For WOCBP, the serum pregnancy test at Visit 1 must be performed at least 3 weeks before the urine pregnancy test performed at Visit 2 prior to randomization.

The intervals between Visit 4 (Week 4), Visit 5 (Week 8) and Visit 6 (EOT) should not exceed 36 days.

(1) History of positive ANA / anti-ds DNA antibodies will be included.

(2) Complete physical examination (i.e., inspection, percussion, palpation and auscultation) will be performed at Visit 1 (Screening) and Visit 6 (EOT). A symptom-driven, abbreviated physical examination will be performed at all other visits in order to capture assessments needed for the SLEDAI-2K

(3) Height only at Screening.

- (4) A chest X-ray that has been performed within 3 months prior to Screening can be used (in this case, no need to repeat chest X-ray at Screening).

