### ***1.3.2.1 Clinical pharmacokinetics***

Following administration of single doses to male healthy subjects, the PK profile of ACT-334441 was characterized by low inter-subject variability (coefficient of variation [CV] < 30% for area under the curve, maximum observed plasma concentration [ $C_{\max}$ ], and half life [ $t_{1/2}$ ]).  $C_{\max}$  was achieved within 5–6 h after dosing and  $t_{1/2}$  was between 170 and 199 h (~ 7–9 days).

Following administration of multiple once daily (o.d.) doses, steady-state conditions were attained between 20–32 days of treatment, and the  $t_{1/2}$  after the last administration was between 12–22 days. ACT-334441 accumulated in plasma, with 5- to 9-fold higher  $C_{\max}$  and area under the curve from 0 to 24 hours ( $AUC_{0-24}$ ) at steady-state when compared to the first day of treatment.  $C_{\max}$  and  $AUC_{0-24}$  were shown to be dose proportional across the 0.5–4 mg dose range.

The effect of food on the PK of a single 1 mg dose was investigated in study AC-064-101. No relevant effect of food on the PK parameters of ACT-334441 was observed.

Only limited clinical data are currently available regarding the metabolism of ACT-334441. No information is available regarding the effects of disease (e.g., renal or hepatic impairment), age, or ethnicity on the PK of ACT-334441. Only limited data are available on the effects of sex on the PK of ACT-334441 (examination of the data from the 2 female subjects who received ACT-334441 suggest that the PK profile is not influenced by sex).

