#### *11.4.3.1.4 Post-treatment AEs and SAEs*

Post-treatment (S)AEs occurring over 6 weeks after treatment discontinuation will be summarized in a similar manner as described in Section [11.4.3.1.1](#).

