#### *11.4.3.1.5 Deaths*

Fatal SAEs occurring any time after the start of treatment will be summarized in a similar manner as described in Section [11.4.3.1.1](#).

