#### **10.9.1 Adverse events**

All AEs captured from signature of informed consent up to EOS are reported in the subject listings which include data collected in eCRF as well as the coded terms (SOC, PT) and a flag for treatment-emergent.

For displays of AEs summarizing counts on the event level (i.e. total number of events), the denominator for calculating percentage is the number AEs occurring in a given treatment group. For displays of events by period of onset, the denominator is the number of AEs occurring in a given treatment group during the relevant period of onset. For displays of AEs summarizing counts on the subject level (i.e. total number of subjects experiencing events), the denominator for percentages is the number of subjects in the SAF for a given treatment group.

For all tables, aggregate counts for total number of subjects, events and associated percentages, and total number of subjects, events and associated percentages per SOC and PT are also included (as applicable).

For tables presented by SOC and PT, SOCs/PTs are sorted by descending frequency of the number of subjects in the highest-dose group. If the frequencies of SOCs or PTs are the same, alphabetical order is used.

For tables presented by PT, PTs are sorted by descending frequency of the number of subjects in the highest-dose treatment group. If the frequencies of PTs are the same, alphabetical order is used.

The following displays of adverse events are provided:

- An overview of treatment-emergent adverse events (TEAEs) by treatment group with the following counts and percentages:
  - Subjects with at least one TEAE;
  - Subjects with at least one serious TEAE;
  - Subjects with fatal serious TEAE;
  - Subjects with at least one non-serious TEAE;
  - Subjects with at least one severe TEAE;
  - Subjects with at least one drug-related TEAE;
  - Subjects with at least one drug-related serious TEAE;
  - Subjects with at least one TEAE leading to study drug discontinuation.
- The number and percentage of TEAEs, and subjects experiencing TEAEs, by period of onset (on Day 1 post-dose, after Day 1, overall), treatment group, SOC and PT.
- The number and percentage of subjects with TEAEs by treatment group and PT.
- The number and percentage of subjects with related TEAEs, by treatment group and PT. If an adverse event (PT) occurs more than once for a subject during the treatment period, the strongest relationship to study treatment is taken into account.

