## 10.9.2 Deaths and other serious adverse events

### 10.9.2.1 Death

#### All deaths

The number and percentage of subjects who died after the start of the treatment are summarized per treatment group, including the reported causes of death. A listing including all deaths is provided.

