### ***Death variables***

**Date of Death** is extracted from the DS domain, where there is a record with Standardized Disposition Term equal to DEATH.

**Death Relative Day to EOT** is computed as the number of days between the date of first exposure to treatment and the end of treatment date.

**Death Relative Day** is computed as the number of days between the date of first exposure to treatment and the date of death.

**Death Dictionary-Derived Term** is extracted from the Death Details domain. It is equal to 'Character Result/Finding in Std Format' where Death Detail Assessment Name equals to Primary Diagnosis.

**Death Reported Term** is extracted from the Death Details domain. It is equal to Result or Finding as Collected where Death Detail Assessment Name equals to Primary Diagnosis.

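### The SAP names no source, cut-off or display for SAEs between 6 and 16 weeks after treatment that the protocol says will be summarised, and its Death Relative Day to EOT omits the date of death

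*Protocol*

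**What the plan says.** **Collection.** Protocol 10.2.2 makes SAEs reportable to drug safety for 16 weeks after treatment but requires them on the eCRF AE pages only for the first 6. Section 8.3.2 says of the two telephone visits: "Note that the data reported at these visits will not be entered in the eCRF". It routes SAEs learned of there to the drug safety department, to be shown apart from the rest in the study report. Protocol Table 1, repeated as SAP Table 2, has a cross for SAEs at Visits 8 and 9 in a row carrying a single asterisk, which the footnote explains as "Data collected in the eCRF".

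**Promised analyses.** Protocol 11.4.3.1.4: "Post-treatment (S)AEs occurring over 6 weeks after treatment discontinuation will be summarized", in the manner of the treatment-emergent tables, which are by dose. Protocol 11.4.3.1.5: "Fatal SAEs occurring any time after the start of treatment will be summarized", in the same manner.

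**SAP.** Section 1 names the SDTM datasets as source data. Section 5.8.1 has AEs recorded on the eCRF up to the EOS visit, and Section 7.1.4 limits safety-set data to EOS unless otherwise stated. Section 10.9.1: "All AEs captured from signature of informed consent up to EOS are reported in the subject listings". Section 5.8.3.1 identifies fatal SAEs from the AE eCRF. Section 10.9.2.1 has a death table without an upper time limit: "The number and percentage of subjects who died after the start of the treatment are summarized per treatment group". Section 5.8.2.1 feeds deaths from a Death eCRF page. Section 11.2.2 says of the variable Death Relative Day to EOT that it "is computed as the number of days between the date of first exposure to treatment and the end of treatment date".

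**The concern.** A late SAE is collected under one rule, promised a table under a second, and analysed under a SAP that stops at EOS. If nobody specifies how the safety-database records reach the report, the by-dose summary in Protocol 11.4.3.1.4 may not be produced, and a death table described without a time limit may be incomplete for deaths first learned of by telephone. The contradiction over eCRF entry could also make ascertainment differ between sites.

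The period is not pharmacologically empty. Protocol 1.3.2.1 reports that, with repeated dosing in healthy subjects, the half-life "after the last administration was between 12–22 days", so some drug is still expected at 6 weeks.

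The date formula is a separate matter. A variable meant to place a death relative to the end of treatment should move with the date of death, and this one does not.

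**Working it through.** No sample size or power figure is involved. The check is a trace of the data flow and a literal evaluation of the formula.

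**1. Length of the unspecified window.** SAE follow-up is 16 weeks (Protocol 10.2.2) and required eCRF AE entry is 6 weeks (same section). 16 − 6 = 10 weeks, and 10/16 = 62.5% of the post-treatment follow-up. This is a share of time, not a count of events.

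**2. Post-treatment (S)AE summary.** Protocol 11.4.3.1.4 promises it. SAP 10.9.1 to 10.9.2.4 describe displays by period of onset only as Day 1, after Day 1 and overall; none is for onset beyond 6 weeks. SAP 4.1 lists changes to the PD set, the per-protocol set and the AESI categories, but not this one. SAP 4.2 reports no change in conduct or data collection.

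**3. Fatal SAEs.** Protocol 11.4.3.1.5 sets no upper limit. SAP 5.8.3.1 reads them from the AE eCRF, where entry is required only to 6 weeks. A fatal SAE in Weeks 7 to 16 therefore has no assured path into that table.

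**4. All deaths.** SAP 10.9.2.1 has no upper limit, and SAP 5.8.2.1 gives no closing date for the Death page. Protocol 8.3.2 keeps telephone-visit data out of the eCRF. Together these leave the route for a death learned of by telephone unclear.

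**5. What each instruction produces.** A site following 8.3.2 enters nothing from Visits 8 and 9. A site following Table 1 enters the SAE. SAP 5.8.1.1 describes treatment-emergent events as running to EOS, but its operative rule, and the derivation in SAP 11.2.7, have no end date. A late SAE entered by the second site would then be counted as treatment-emergent.

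**6. Residual drug at 6 weeks.** Assuming simple exponential decline, the remaining fraction is 2^(−42/t½). For t½ = 12 days, 2^(−3.5) = 0.088; for t½ = 22 days, 2^(−1.91) = 0.266. About 9% to 27% remains.

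**7. The death formula.** As written it is end-of-treatment date minus first exposure date, the same words as End of Treatment Day in the same section. SAP 11.1.1 defines a day relative to EOT differently, as days since last intake. The example assumes that the last dose falls on the end-of-treatment date:

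| Weeks from last dose to death | Death date − last intake (days) | SAP formula, 84 days treated | SAP formula, 28 days treated |
|---|---|---|---|
| 1 | 7 | 83 | 27 |
| 6 | 42 | 83 | 27 |
| 11 | 77 | 83 | 27 |
| 16 | 112 | 83 | 27 |

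The SAP value is constant in the date of death and always equals End of Treatment Day.

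**The case against.** The split between eCRF and safety database looks deliberate. Protocol 8.3.2 gives late SAEs a destination in the study report, 10.2.2 states the 6-week and 16-week limits together, and 10.3.2 handles pregnancies in the same way. A reader might infer that these SAEs have no route into the report at all; the documents do not support that. What stands is that Protocol 11.1 says the SAPs give full details of analyses and displays, and this SAP gives none for that presentation.

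A reader might also infer that the death table misses late deaths. That is not shown: nothing closes the Death page at EOS, and the table has no upper limit. Nor is it shown that the ten weeks lie outside every SAP safety table. The operative treatment-emergent rule has no end date, so late SAEs that reach the eCRF would be counted.

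It is tempting to say that the 16-week follow-up exists to catch late infections and malignancies. Protocol 3.2 says only that the calls further increase patients' safety. It justifies the 6-week visit by lymphocyte counts normalising within 28 days at 4 mg in healthy volunteers, which tempers the residual-drug argument.

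Two further points are fair. SAP Section 13, the list of outputs, shows no contents in the public copy, so the absence of a table rests on Section 10.9. And no display described in SAP 10.9.2.1 uses Death Relative Day to EOT, so that error affects a dataset column and not the death counts.

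**Conclusion.** The point holds as a gap in specification. The SAP does not implement the protocol's summary of (S)AEs more than 6 weeks after treatment and cannot assure its summary of fatal SAEs at any time; Section 4 does not declare either departure. Completeness of the all-deaths table for deaths first learned of by telephone is unassured, but not disproved. The schedule tables and Protocol 8.3.2 contradict each other on whether the same SAEs enter the eCRF.

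The gap covers 10 of 16 post-treatment weeks. The number of events affected cannot be known from the documents. The 9% to 27% residual drug rests on healthy-subject half-lives and simple exponential decline. The formula error is certain, needs no assumption beyond reading the definition literally, and has a narrow effect. None of this touches the lymphocyte-count analysis.

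**What to change.** 1. Reconcile Protocol Table 1 and SAP Table 2 with Protocol 8.3.2 and 10.2.2, so that sites have one instruction on entering Visit 8 and 9 SAEs.
2. In SAP 10.9.2, name the source for SAEs and deaths after EOS (eCRF, or the safety database after reconciliation) and the cut-off. Add the protocol's by-arm summary of SAEs and deaths with onset more than 6 and up to 16 weeks after last intake, and state that the all-deaths table draws on the same source. Keep these events apart from treatment-emergent ones by giving the derivations in SAP 5.8.1.1 and 11.2.7 their 6-week/EOS upper limit. If the summary is instead to be dropped, SAP Section 4 must say so and why.
3. In SAP 11.2.2, define Death Relative Day to EOT as date of death minus date of last study treatment intake, matching SAP 11.1.1.

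The cost is SAP and schedule wording, one table and a reconciliation step. The downside is timing: the late-event table is final only after the last Week 16 call, about 10 weeks after the last EOS visit, whereas Protocol 9.1 places study-level EOS at the completion of the EOS visits.
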